**13E. Describe the expected benefits of the research to the subjects and/or to society.**

The potential benefits to participants in this study and other members of the community are significant and may be long lasting. Significant short-term benefits include detecting and treating cases of COVID-19 and preventing further transmission of the disease. While participants are enrolled in the study, referrals to resources to address social determinants of health (e.g., housing, food insecurity) may provide immediate tangible benefits. In addition, if participants express a need for mental health assistance at any time, the project team and the ICCB are well equipped to either provide service or make appropriate referrals. After engaging in the interventions, participants may experience increased feelings of empowerment and self-esteem, both of which have been associated with improved health outcomes. If the study succeeds in reducing medical mistrust and increasing health literacy, those benefits may be long-lasting. Both the short-term and long-term potential benefits of this study justify the potential risks involved in participation.

13F. Weigh the risks with regard to the benefits. Provide evidence that benefits outweigh risks.

Knowledge to be gained from this investigation is important for understanding and addressing COVID-19 morbidity and mortality disparities and potential barriers to testing among medically and socially vulnerable populations. The opportunity to engage residents of East St. Louis, IL in the proposed adaptive interventions is an opportunity to increase health literacy and reduce medical mistrust among a severely underserved population. This is vitally important in light of the contradictory and constantly changing information about COVID-19 being disseminated by federal and state governments and mass media. Moreover, because the knowledge generated by this study will be shared with other members of the RADx-UP consortium, it has the potential to improve access to prevention strategies, testing and treatment in vulnerable communities across the country. The value of the knowledge to be gained far outweigh the potential risks of participation described above, particularly when considering the precautions we have taken to minimize these risks. Although participants' risk of experiencing COVID-19 related distress is real, involvement in the study can also reduce fear and anxiety. As explained earlier, project staff will employ every effort to maintain confidentiality and to minimize any other potential risks; should a serious adverse event occur, it will be reported to the DSMB, Project Officer, funding agencies and the UIUC IRB within 48 hours. Adverse events will be tracked in a database and reviewed at each DSMB meeting. Our CBPR research to date indicates that community members themselves will be committed to assisting us in the successful and safe implementation of this project.

Section 14. INFORMED CONSENT PROCESS TO INCLUDE: WAIVERS, ASSENTS, ALTERATIONS, ETC.**14A. Indicate all that apply for the consent/assent/parental permission process.**

 Written informed consent (assent) with a document signed by		
 adult subjects	 parent(s) or guardian(s)	 adolescents aged 8–17 years
 Waiver of Documentation (signature) of Informed Consent (include the relevant Waiver Form)		
 adult subjects	 parent(s) or guardian(s)	 adolescents aged 8–17 years
 Waiver of Informed Consent (include the relevant Waiver Form)		
 adult subjects	 parent(s) or guardian(s)	 adolescents aged 8–17 years

Alteration of Informed Consent (*include the relevant [Alteration Form](#)*)
 adult subjects parent(s) or guardian(s) adolescents aged 8–17 years

14B. List all researchers who will obtain consent/assent/parental permission from participants.

Researchers who may participate in obtaining consent include the PIs ([name] & [name]), project coordinator, study outreach workers and research assistants at CBHC that will be trained and approved as members of the research team by the UIUC IRB. Note we have not yet hired the project coordinator nor the peer navigators. Staff will be added to the protocol as they are hired and complete their IRB training. Only staff that have been approved by the IRB will have contact with study participants.

14C. Describe the method for obtaining consent/assent/parental permission. Eligible individuals will provide written informed consent before participating in the study. During the informed consent process, the study outreach worker or research assistant will explain the study design in detail, including its purpose, the source of funding, why individuals are invited to participate, what they will be asked to do, how long the study will last and how many people are expected to take part in the study. They will explain the processes of SARS antigen testing at CBHC and randomization, the interventions being tested, potential sources of risk and discomfort and measures designed to minimize both. They will answer all participant questions and will ask participants to describe in their own words what they expect to do in the study before obtaining signatures. Participants who do not comprehend the study description will not be enrolled. Participants who would like some time to think before deciding will be able to take informed consent material home with them for review and consideration. All participants who provide written consent will receive a copy of the consent document which, in addition to the study description outlined above, includes names and contact information (phone numbers and email) for the Principal Investigators and for the appropriate ethics officials at the University of Illinois Urbana-Champaign, the grantee institution.

14D. Describe when consent/assent/parental permission will be obtained. Consent will be obtained through a RedCAP survey that participants can complete online or at CBHC.

14E. Will participants receive a copy of the consent form for their records?

Yes No, if no, explain:

14F. Indicate factors that may interfere or influence the collection of voluntary informed consent/assent/parental permission.

No known factors
 Research will involve students enrolled in a course or program taught by a member of the research team
 Research will involve employees whose supervisor(s) is/are recruiting participants
 Participants have a close relationship to the research team

Other, specify any relationship that exists between the research team and participants:

If applicable, describe the procedures to mitigate the above factors.

14G. Copies of the consent form(s) are attached. Yes Not applicable

14H. Will this project be registered as a clinical trial? Yes No

If yes, effective January 21, 2019, an informed consent form must be posted on the Federal Web site after the clinical trial is closed to recruitment, and no later than 60 days after the last study visit.

Section 15. DEVICES & DRUGS

Indicate if your research includes any of the following.

Equipment [Researchers collecting physiological data, not testing the device]
(include Appendix A, the [Research Equipment Form](#))

Devices [Researchers planning to test devices on human subjects]
(include Appendix B, the [Device Form](#))

Materials of Human Origin
(include Appendix C, the [Biological Materials Form](#))

Drugs and Biologics
(include Appendix D, the [Drug and Chemical Usage Form](#))

MRI AT BIC To use the [Beckman Institute Biomedical Imaging Center](#) (BIC) in human subject's research, you must obtain prior approval from the BIC [contact]; [contact]) and use BIC-approved screening and consent forms. Attach:

BIC approval BIC screening form BIC consent form

Section 16. CONFIDENTIALITY OF DATA & PRIVACY OF PARTICIPATION

16A. How is participant data, records, or specimens identified when received or collected by researchers? Identifiers include, but are not limited to, name, date of birth, email address, street address, phone number, audio or video recordings, and SSN.

No identifiers are collected

Direct identifiers are collected

Indirect identifiers (e.g. a code or pseudonym used to track participants);
Does the research team have access to the identity key? Yes No

16B. Select all methods used to safeguard research records during storage:

Written consent, assent, or parental permission forms are stored separately from the data

Data is collected or given to research team without identifiers

Data is recorded by research team without identifiers

Direct identifiers are removed from collected data as soon as possible

Direct identifiers are deleted and no identity key exists as soon as possible

Participant codes or pseudonyms are used on all data and the existing identity key is stored separately from the data

Electronic data is stored in a secure, [UIUC-approved location](#), please specify REDCAP and Box Health

 Hard-copy data is stored in a secure location on UIUC's campus, please specify  Other, please specify :	
16C. How long will identifiable data be kept? All identifying electronic data will be destroyed immediately after data collection is completed. Audio recordings will be kept for 3 years after study completion. De-identified data including COVID-19 test results will be kept indefinitely.	
16D. Describe provisions to protect the privacy interests of subjects. In addition to the creation of and ongoing adherence to the DSMP and the procedures indicated earlier in this protocol, participants will be protected by a Certificate of Confidentiality issued by the NIH. Under terms of the Certificate, the researchers cannot be forced to disclose information that may identify a participant, even by a court subpoena, in any federal, state, or local civil, criminal, administrative, legislative, or other proceedings. However, the Certificate cannot be used to resist a demand from United States Government personnel for information that is used for auditing or evaluation of federally funded projects or for information that must be disclosed in order to meet the requirements of the federal Food and Drug Administration (FDA). Researchers may also disclose the identity of participants who report intentions to harm themselves or others or if researchers have knowledge those participants are abusing children or elderly persons.	

In order to further protect participants' privacy from having a navigator see their baseline information without their written consent, we will program Redcap to automatically only produce the navigation baseline report if the participant checked the yes box in the consent form. This way, navigators will only be able to see the relevant COVID-19 risk information baseline report if the participant provided written consent.
 
HIPPA protected data will be stored in Redcap and Box Health. All research members with access to this information will complete a HIPPA training prior to accessing the data. Weekly staff meeting will be used to remind staff of confidentiality and HIPPA data protection protocol.
	
16E. Describe the training and experience of all persons who will collect or have access to the data. All members of the research team will complete the required CITI training and will be trained on this specific study protocol by the principal investigators. Drs. [name], [name], and [name] have extensive experience conducting similar studies and adhere to best practices in data collection and retention. [name], as a trained social worker and executive director of CHBC, has decades of experience in service provision, client rights and privacy, and administration of federally funded programs. Once a new research team member is hired, as part of the onboarding process at CSBH, they must complete a variety of standardized trainings on confidentiality, COVID-19, and IT security. Additionally, research team members will receive training on tasks that are specific to their job expectations. Everyone will receive training on Redcap (1 hour online and homework tutorials and practices), human subjects research (CITI training), COVID-19 protocol (1 hour and ongoing training during weekly meetings), and on study protocols (includes professionalism, confidentiality, cultural humility, referral making, safety procedures). Street outreach staff will also receive training on safety while working in the field, confidentiality in the field, how to complete the study screener, and dos and don'ts when calling	

participants (2 hours plus homework and role plays). Peer Navigators will complete an online training on Motivational Interviewing with a professional trainer (8 hours plus homework and role plays). They will also complete a 2 hour training on Navigation Services with [name]. They will be paired with [name], the seasoned peer navigator from New Jersey for mentorship and extra support. They will have ongoing clinical supervision weekly meetings with [name] to review their cases, ensure fidelity, and review study protocols. The Critical Dialogue facilitator will be trained by [name] including a period of shadowing the facilitations, role plays, and observations, until they are approved to run the sessions on their own. Finally, during staff meetings we continually identify possible training gaps and make sure these are addressed as needed. Particularly with the changes on COVID-19 recommendations, we often use the weekly meetings to review the protocol, make sure it is up to date, and that everyone has the same understanding. All of this is tracked in minutes that are recorded and saved after each meeting. This includes a table that reflects the training and the dates in which each staff completed it.

Section 17. DISSEMINATION OF RESULTS

17A. List proposed forms of dissemination (e.g. journal articles, thesis, academic paper, conference presentation, sharing within industry, etc.).

The proposed study is purposefully planned with rapid translation, dissemination and sustainability in mind. The adaptive intervention is envisioned as an efficient and effective model that can ultimately be replicated in the field and scaled-up with high fidelity. Beginning in the research planning stage, and iteratively throughout all phases of the study, we are ensuring that the manual, once efficacious, can be disseminated among service providers across similar settings. The Collaborative Board will design a comprehensive plan to disseminate the study findings to the community at large.

Consistent with NIH policy, the PIs in the proposed application will make the data available, on appropriate terms and conditions, to the research community in a timely manner. We will follow the NIH Policy on the Dissemination of NIH-Funded Clinical Trial Information NOT-OD-16-149. The study will be registered under the Clinical Trials Registration at ClinicalTrials.gov for public posting. The study will be registered within 21 calendar days after the enrollment of the first participant, results will be submitted no later than one year after the completion of final data collection, and all required elements will be provided. Results including participant flow, demographic and baseline characteristics, outcomes and statistical analyses, adverse events, the protocol and statistical analysis plan, and administrative information will be updated on ClinicalTrials.gov bi-annually (twice each study year).

17B. Will any identifiers be published, shared, or otherwise disseminated? Yes No

If yes, does the consent form explicitly ask consent for such dissemination, or otherwise inform participants that it is required in order to participate in the study? Yes

17C. Do you intend to put de-identified data in a data repository? Yes No

If yes, explain how data will be de-identified. We will download only de-identified data from Redcap. Redcap flags any variable that contains identifiable information. We can then have the software exclude these variables automatically. The data will be exported by a doctoral student and checked by [name], our statistician. Moreover, the Duke data repository has additional data quality checks to make sure no identifiable information is uploaded into the system.

Section 18. INVESTIGATOR & DEPARTMENTAL ASSURANCES

- I certify that the information provided in this application is complete and correct.
- I certify that I will follow my IRB Approved Protocol.
- I accept ultimate responsibility for the conduct of this study, the ethical performance of the project, and the protection of the rights and welfare of the human subjects who are directly or indirectly involved in this project.
- I will comply with all applicable federal, state and local laws regarding the protection of human subjects in research.
- I will ensure that the personnel performing this study are qualified and adhere to the provisions of this IRB-certified protocol.

COVID-19 Treatment Cascade Optimization Study

NCT05305443

Statistical Analysis Plan

3/30/2022

Statistical Analysis Plan

Data analysis: Aim 1. We will estimate the (1) differences in the effects of first-stage interventions (NS vs brochure), (2) differences in the effects of second-stage interventions (BC vs NS among those who complete testing and referral vs CD among testing decliners), and (3) differences in the effects of selected adaptive interventions on acceptance of testing and adherence to IL recommendations. For differences between NS and brochure, cross-tabulations of the interventions with each outcome will be generated, and crude odds ratios comparing the two will be calculated. For the effects of second-stage and third-stage interventions, we will perform a similar analysis as that for the first-stage interventions but on corresponding subsets as indicated in the specific comparison groups. The estimation of effects of embedded adaptive interventions will use weighted and replicated estimation techniques. Under these procedures, the data set will be restructured wherein an individual's outcome will be replicated in the data set depending on the number of adaptive interventions consistent with this outcome. Since randomization at both stages is based on equal probabilities, weighing is not necessary. The restructuring of the data set as described allows the utilization of standard statistical software for parameter estimation and hypothesis testing. A generalized linear model using logistic regression will be performed where estimation of model parameters will be done using generalized estimating equations due to the presence of replicated subjects. We will then use tests of contrasts to compare selected adaptive interventions. The analysis of the adaptive interventions will be done using PROC GENMOD in SAS. To adjust for baseline characteristics and test for their moderating effects, we will incorporate these terms and their interactions with first-stage, second-stage, and adaptive interventions in their respective models. Only the baseline characteristics will be used for adjustment, as outcomes of the first-stage intervention are biased if incorporated into this model. Odds ratios, 95% CI, and Wald's test for the effect of interventions and covariates will be obtained from these results. Sex/gender and race/ ethnicity will be among these covariates that we will consider for adjustment and moderation analysis.

Interim analyses

An interim analysis will be conducted bi-monthly by study analysts once data collection starts. This will include the development of syntax to clean the data (e.g., missingness analysis, identification of data entry errors, recoding variables). The key variables will be reviewed. Descriptive data will be presented to PIs and members of the NCCB. The NCCB will review preliminary findings presented by the PIs on a bi-monthly basis to address any potential adverse reactions that may occur and any safety concerns that may arise. If any participants are found to be unresponsive to the intervention, or getting worse during the course of the study, an NCCB sub-committee will discuss the case and the participant may be terminated from the study and referred to relevant services in the community. The PIs will meet weekly with the study staff to review the study protocol adherence and address any potential problems. The PIs will also have weekly supervision meetings with intervention facilitators to review the results from fidelity ratings and address any potential deviance from interventions.

Methods for additional analyses (e.g., subgroup analyses)

Aim 2: To identify other predictors of these outcomes, we will include these variables as covariates using logistic regression analysis. We will model probabilities of testing behavior (completed vs testing decliners) and adherence to IL recommendations as functions of the first-stage intervention and other covariates in the logistic regression analysis.

Qualitative component analysis: Critical dialog sessions and in-depth interviews will be digitally audio-recorded and transcribed. Data will be entered into Atlas ti, a qualitative data processing program. Analysis rooted in phenomenology and grounded theory will include continuous coding, comparison, and recoding to yield categories and connect experiences and themes. The analysis will focus on participant reports about their experiences with the intervention, barriers to testing and adherence to IL recommendations, and suggestions on how to address these barriers.

Methods in analysis to handle protocol non-adherence and any statistical methods to handle missing data

We will perform an intent-to-treat analysis of the data. Subjects will be grouped according to how they are randomized. The multiple imputation strategy described will be adapted. This uses a time-ordered nested conditional imputation strategy with multiple imputation of missing values. In this approach, the fully conditional specification (FCS) imputation framework wherein a separate model for each variable is fitted will be applied. We will consider the time ordering of the data. For example, observed baseline variables will be used to impute for missing data from the first-stage results. Then, the imputed and observed values of the first-stage results will be used in conjunction with baseline variables to impute missing values for the second-stage results. We will examine the distribution of missing data according to intervention groups, covariates (e.g., demo-graphic characteristics, adherence, reason for discontinuation), outcome variables, and time. We will determine whether the missing data pattern is not inconsistent with the missing-at-random (MAR) mechanism. We will also check whether the amount of missingness is monotonic over time. The R software packages mice and pan will be used for imputation.

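### Aim 1 takes adjusted intervention effects from models that also carry the moderation terms, so without a stated coding or averaging contrast they may describe only a reference subgroup

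*SAP*

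**What the plan says.** The SAP, under Data analysis: Aim 1, describes two layers of analysis.

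- **Unadjusted.** For navigation against brochure, "cross-tabulations of the interventions with each outcome will be generated, and crude odds ratios comparing the two will be calculated". For later stages, "we will perform a similar analysis as that for the first-stage interventions but on corresponding subsets". For the embedded adaptive interventions, a logistic model is fitted by GEE on the replicated data set, and then: "We will then use tests of contrasts to compare selected adaptive interventions".
- **Adjusted and moderated.** To adjust for baseline characteristics and to test whether they moderate the effect, "we will incorporate these terms and their interactions with first-stage, second-stage, and adaptive interventions in their respective models". Of the covariates it says: "Sex/gender and race/ ethnicity will be among these covariates that we will consider for adjustment and moderation analysis". The reported quantities follow: "Odds ratios, 95% CI, and Wald's test for the effect of interventions and covariates will be obtained from these results".

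For the second layer the SAP gives no coding, no centring, no contrast coefficients and no covariate values at which an effect is evaluated. It does not say which layer is primary. Protocol section 6A, primary aim 1, commits the analysis to controlling for baseline, time, demographics and COVID risk.

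**The concern.** Adjustment and moderation call for different models. Adjustment asks for one intervention effect with covariates held fixed. Moderation asks whether that effect varies across covariate levels. Once the product terms are in, there is no longer a single intervention effect: the coefficient labelled as the intervention is the effect where every moderator is at zero. Under reference coding, that is for example one sex within one race/ethnicity group.

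Two things are at stake. The adjusted result could answer a narrower question than Aim 1 poses and shift with an arbitrary choice of reference category. It would also be estimated with less precision than the overall effect. The choice would be left to the analyst, in a study where descriptive data are shown to the investigators bi-monthly (SAP, Interim analyses).

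**Working it through.** **Inputs**

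- Model content and source of the reported effects: SAP Aim 1, as quoted above. Coding and contrast weights: not stated.
- Power, event rates and effect size: none stated, so there is no plan figure to reproduce. I assume 80% power for the average effect and two-sided 0.05, the latter inferred from "Odds ratios, 95% CI, and Wald's test".
- Allocation: equal at each stage (SAP).
- Sample: 670 + 548 = 1,218 (Protocol 6A). Planned sex split: 580 men and 636 women overall, 252 and 295 in Illinois (Protocol 9A; the overall split sums to 1,216, which is immaterial here).
- Moderators: sex/gender and race/ethnicity are named. Their full number and their shares are not given, so these are assumed.

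**Step 1: what the coefficient means.** Write logit P = a + bT + Σ c_k Z_k + Σ d_k T·Z_k, with Z_k = 0 at the reference level and p_k the non-reference share of moderator k. The effect in the reference cell is b. The effect averaged over the sample is b + Σ d_k p_k. Centring each Z_k at p_k makes b equal to that average. The model is the same in both cases; only the reported combination differs.

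**Step 2: precision of b.** With independent binary moderators and two-way products only, SE inflation relative to the overall effect is √(1 + Σ p_k/(1 − p_k)). With equal true effects, power = Φ((1.96 + 0.842)/inflation − 1.96).

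- One 50/50 moderator: √2 = 1.41; Φ(0.02) = 51%.
- Two: √3 = 1.73; Φ(−0.34) = 37%.
- Three: √4 = 2.00; Φ(−0.56) = 29%.
- Sex 50/50 plus race/ethnicity at an assumed 80/20: with the majority as reference, √(1 + 1 + 0.25) = 1.50, giving 46%; with the minority as reference, √(1 + 1 + 4) = 2.45, giving 21%. The 80/20 split is illustrative; Protocol 10D says only that Black participants are expected to be overrepresented.

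**Step 3: the planned sex counts.** Take an effect with 80% power in all 1,218. Power in one sex alone is 52.5% (636 women) or 48.9% (580 men). For an effect with 80% power in the 548 Illinois participants, it is 53.7% (295 women) or 47.4% (252 men). These figures are the same for assumed control rates of 0.30, 0.40 and 0.50. Starting from 90% power, with a control rate of 0.40, a single-sex reference gives 59–66%.

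**Step 4: simulation.** Logistic regression with one binary covariate, equal true effects, control rate 0.40, 2,000 runs per setting (Monte Carlo SE near 80% is √(0.8 × 0.2/2,000) = 0.9 points). Power:

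| N | Reference share | Reference coefficient | Equal-weight contrast | Size-weighted contrast | No interaction |
|---|---|---|---|---|---|
| 1,218 | 50% | 51% | 80% | 80% | 80% |
| 1,218 | 25% | 29% | 69% | 80% | 80% |
| 548 | 50% | 50% | 80% | 80% | 80% |
| 548 | 25% | 28% | 66% | 78% | 78% |

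The loss belongs to the reference coefficient. The size-weighted contrast from the same interaction model matches the model without interactions. The simulation used ordinary logistic regression, not GEE on replicated records, so it carries over to the embedded interventions by analogy only.

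**The case against.** The strongest defence is that Aim 1 already contains overall effects free of interactions. Crude odds ratios are planned at each stage, and the embedded interventions are compared by GEE contrasts before covariates enter. Under randomization these are valid estimates of average effects. This stands, but it does not settle the matter: Protocol 6A promises covariate control, so an adjusted estimate is owed as well.

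A reader might infer that the Aim 1 models supply the only adjusted intervention test in the plan. They do not. The SAP's Aim 2, under methods for additional analyses, models testing and adherence on the first-stage arm plus other covariates, with no interactions mentioned. Its stated purpose is to find predictors and it covers the first stage only, but it narrows the gap to adjusted second-stage and embedded effects.

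A reader might also infer that interactions by themselves force a reference-subgroup test with a large loss of power. They do not. That result needs reference coding and a raw coefficient read off the output. The SAP specifies neither, and for adaptive interventions it names contrasts. It is also fair to say that the sentence on odds ratios could refer to all the models in the paragraph, and that the wording does not exclude fitting adjustment before moderation. What remains is that nothing in the text says so, and that the nearest models to that sentence contain the interactions.

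**Conclusion.** The point holds in conditional form. Aim 1 merges adjustment and moderation in one model per comparison and takes the intervention effects from it without defining which effect is meant. If the coefficient is read under reference coding, the adjusted effect is that of a reference subgroup. The exposure is mainly in the adjusted second-stage and embedded adaptive-intervention comparisons.

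The power figures of 51%, 37% and 29% illustrate the possible cost. They are not properties of this trial, because they rest on an assumed 80% benchmark, assumed moderator shares, independence, equal true effects and reference coding. If the true effects differ between subgroups, the reference coefficient also targets a different quantity from the average. This should be changed before analysis; it does not invalidate the unadjusted comparisons.

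**What to change.** Separate the two purposes in the Aim 1 text.

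1. Report adjusted intervention odds ratios, 95% confidence intervals and Wald tests from a logistic or GEE model with the intervention terms and baseline covariates as main effects only. An acceptable alternative is a prespecified contrast from the interaction model, averaged over the sample covariate distribution. Equal weighting across levels is less suitable when a covariate is unbalanced (66–69% power in the 25% reference-share rows of the simulation).
2. Fit the covariate-by-intervention interactions in a second model, used only for moderation tests and subgroup estimates.
3. State the covariate coding, list the covariates, and say whether the crude or the adjusted estimate is primary for each comparison.

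The cost is a few sentences in the SAP and one extra model fit per comparison. No design or data-collection change is needed.
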